LC-MS/MS Liquid chromatography mass spectrometry

LEAP Leishmaniasis East Africa Platform

MedDRA Medical Dictionary for Regulatory Activities

MF Miltefosine

MoH Ministry of Health

MUAC Mid Upper Arm Circumference

MSF Medecins Sans Frontières (Doctors without Borders)

NCE(s) New Chemical Entity(ies)
PCR Polymerase chain reaction

PD Pharmacodynamic
PI Principal investigator
PK Pharmacokinetics

PKDL Post Kala azar Dermal Leishmaniasis

PM Paromomycin PP Per Protocol

Confidential Page 12 of 68

PT Prothrombin Time

QD (q.d.) Daily

RDT Rapid Diagnostic Test SAE Serious adverse event

SOP Standard Operating Procedure

SSG Sodium Stibogluconate

TBIL Total Bilirubin

TEAE Treatment emergent adverse event

ULN Upper limit of normal

VCT Voluntary counselling and testing programme

VL Visceral Leishmaniasis

WBC White blood cell

WHO World Health Organization

Confidential Page 13 of 68

PROTOCOL SYNOPSIS

Protocol title	An Open Label, Phase III, Randomized Controlled, Multicentre Non- Inferiority Trial to Compare Efficacy and Safety of Miltefosine and Paromomycin with Sodium Stibogluconate and Paromomycin Combination for Treatment of Primary Visceral Leishmaniasis (VL) Patients in Eastern Africa								
Short title	MF/PM Phase III								
Clinical Trial Protocol Number	DNDi-MILT/PM-01-VL								
Sponsor	DND i , [name]. [contact]								

PROTOCOL SUMMARY

Current WHO-recommended treatment for Visceral Leishmaniasis (VL) in Eastern Africa is a combination of Sodium Stibogluconate (SSG) and paromomycin (PM) administered for 17 days, with an efficacy of 91%. This treatment is far from optimal as it requires 17 days of two separate painful injections, necessitating patients to be hospitalized during the whole treatment period. In addition, the antimonial SSG exhibits life-threatening toxicities such as cardiotoxicity, hepatotoxicity and pancreatitis. Therefore, there is an urgent need to explore alternatives that are efficacious, safe, ideally of short duration, affordable and suitable to be used in remote areas where VL occurs.

Until new chemical entities are developped, opportunities with currently available compounds should be assessed to improve on current treatment options, with the main aim to replace the toxic and patient-unfriendly SSG treatment-component.

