- 3) Replacement of the primary imputation approach by the realistic approach (LTFU have the same rate of relapse as completers: $P_S = 1 P_R$).
- 4) Replacement of the mITT by the per-protocol set of patients.
- 5) Replacement of the mITT by the set of completers. This analysis avoids any imputation but is based on a subset of patients. The result should be close to the third sensitivity analysis if there are not many patients with unconfirmed status.

Justification of the non-inferiority margin

The non-inferiority margin of 7% has been defined after consultation with experts. It is justified by the following advantages of the tested combination arm over the reference arm: replacing SSG with oral MF will improve treatment safety by removing the toxic antimonial component of the current SSG-PM treatment; it will be a more patient-friendly treatment by replacing one of the two daily injections with an oral administration; and hospitalization time will be reduced by at least 3 days. Finally, the new combination will ensure suitability in remote areas where VL occurs.

Shift from non-inferiority to superiority

If the tested combination is significantly non-inferior to the reference arm, the test of superiority will be performed (Likelihood ratio test) without adjustment of type error.

Confidential Page 57 of 68

The result of this test as well as the 95% confidence interval of the excess success rate will be used to assess the benefit risk of the tested combination with regards to the reference arm but not to claim the superiority. The analysis will be the same as the primary analysis after replacing the non-inferiority test by the superiority.

Interim analysis

No interim analysis (IA) will be performed in this trial.

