10.7. Safety Analysis

All patients enrolled and who received at least one dose of study medication (mITT set of patients) will be included in the safety analysis (treatment-emergent AEs). The incidence rate of the most pertinent and frequent ADR (> 5%) of each treatment group will be compared and tested. No adjustment for multiplicity will be performed. These results will be used for assessing the benefit risk ratio.

The proportion of patients with SAE and/or AEs leading to treatment discontinuation will be described per System Organ Class (using preferred terms defined by MedDRA), and summarised according to relationship to treatment and severity (CTCAE, version 4.03). In addition, a narrative for each of the SAE and AE leading to treatment discontinuation will be developed describing all aspects of the medical event.

The proportion of patients presenting at least one treatment emergent AE (TEAE) will be presented. All TEAEs will be described per study arm using the same classification as presented above. AEs will be tabulated by severity (CTCAE V4.03), and causality.

Abnormalities of laboratory/procedures results will be tabulated with respect to clinical significance. In addition, shift tables and graphs will be generated to describe the laboratory parameter values over time, per treatment arm.

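### Formal between-arm safety testing covers only reactions above 5% and no safety difference gets an interval, so an antimonial toxicity with a true SSG-PM rate below 5% would usually not be formally compared

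*Combined protocol and SAP*

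**What the plan says.** Section 10.7 has one sentence that promises a between-arm test of safety: "The incidence rate of the most pertinent and frequent ADR (> 5%) of each treatment group will be compared and tested". It adds that "No adjustment for multiplicity will be performed" and that "These results will be used for assessing the benefit risk ratio". The test, its significance level and its sidedness are not stated.

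The rest of 10.7 is descriptive. For the most serious events, "The proportion of patients with SAE and/or AEs leading to treatment discontinuation will be described per System Organ Class", and "a narrative for each of the SAE and AE leading to treatment discontinuation will be developed". For the remainder, "All TEAEs will be described per study arm using the same classification as presented above", with no frequency floor. Laboratory values get shift tables and graphs by arm. No risk difference or confidence interval is specified for any safety outcome.

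Under the justification of the non-inferiority margin, Section 10.6 gives several advantages of MF/PM in support of 7%. The first is that "replacing SSG with oral MF will improve treatment safety by removing the toxic antimonial component of the current SSG-PM treatment". The others are one fewer daily injection, at least three fewer hospital days, and suitability for remote areas. The Protocol Summary says what the safety reason refers to: "the antimonial SSG exhibits life-threatening toxicities such as cardiotoxicity, hepatotoxicity and pancreatitis". No incidence is given for any of these toxicities.

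**The concern.** The plan accepts an efficacy loss of up to 7 points partly in exchange for a safety gain. It then limits formal safety comparison to reactions that turn out to be frequent. A cardiac, hepatic or pancreatic toxicity that occurs in a few per cent of SSG-PM patients would be tabulated, but with no planned test or interval to show how large the difference is or how precisely it is known. The same is true of SAEs and discontinuation AEs, which are the first safety endpoint in Section 2.2.2.

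Two features of the rule add to this and do not depend on event rates:

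- Choosing what to test by observed incidence makes the tested list depend on the data, and the trial is open label (Section 7.6).
- The wording does not say in which arm 5% must be exceeded. If it means both arms, a reaction confined to SSG-PM could never qualify.

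At stake is the quality of the benefit-risk assessment that 10.7 says these results will feed. Its formal results could relate only to frequent reactions.

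**Working it through.** **Inputs.** From Section 10.1: 153 patients per arm, 10% provision for loss to follow-up, 170 enrolled per arm. From Section 10.7: the threshold of more than 5%. Assumed, because the documents give no value: the true toxicity rate in each arm, a two-sided Fisher exact test at 0.05, and all 170 patients per arm dosed.

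**Denominator.** 153 / (1 − 0.10) = 170, which reproduces the plan's figure.

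**Threshold as a count.** 0.05 × 170 = 8.5, so more than 5% means at least 9 patients (9/170 = 5.3%).

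**Chance of reaching the tested list.** P(X ≥ 9) with X ~ Binomial(170, p), where p is the true SSG-PM rate:

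| True SSG-PM rate | 1% | 2% | 3% | 4% | 5% | 6% | 8% |
|---|---|---|---|---|---|---|---|
| Reaches 9 of 170 | 0.01% | 0.8% | 7.2% | 24% | 48% | 70% | 93% |

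With 153 patients the cut-off is 8 (8/153 = 5.2%), and the chances at 2%, 3%, 4% and 5% are 1.2%, 9.1%, 27% and 50%. The picture does not change.

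**Power with and without the cut-off.** Exact power is the sum, over all pairs of counts (x in SSG-PM, y in MF/PM), of the product of the two binomial probabilities wherever Fisher p ≤ 0.05. With the cut-off, only pairs with at least 9 events in one arm are kept. This is the lenient reading, above 5% in either arm.

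| SSG-PM rate | MF/PM 0%: with cut-off | MF/PM 0%: without | Points lost | MF/PM one quarter: with cut-off | MF/PM one quarter: without | Points lost |
|---|---|---|---|---|---|---|
| 1% | 0.0% | 0.8% | 0.8 | 0.0% | 0.5% | 0.5 |
| 2% | 0.8% | 12.7% | 11.9 | 0.6% | 6.3% | 5.7 |
| 3% | 7.2% | 40.2% | 33.0 | 5.4% | 17.0% | 11.6 |
| 4% | 24.2% | 67.8% | 43.6 | 16.5% | 28.4% | 11.9 |
| 5% | 47.9% | 85.7% | 37.8 | 30.9% | 39.0% | 8.1 |

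Over 3% to 5%, the loss is 33 to 44 points against an MF/PM rate of 0%, and about 8 to 12 points if MF/PM has one quarter of the SSG-PM rate.

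**Splits that the rule excludes.** With 170 per arm, 6, 7 and 8 events against 0 (3.5%, 4.1% and 4.7%) give two-sided Fisher p = 0.030, 0.015 and 0.007. All three fall below the cut-off.

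**What an interval adds.** Take 5/170 against 0/170. The difference is 2.9 points and Fisher p = 0.061. The Wilson limits are 1.26% to 6.70% for 5/170 and 0% to 2.21% for 0/170. The Newcombe 95% limits for the difference are:

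- lower: 2.94 − √[(2.94 − 1.26)² + 2.21²] = 0.2 points
- upper: 2.94 + √[(6.70 − 2.94)² + 0²] = 6.7 points

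The interval shows which differences the data allow, which is more useful for benefit-risk than a p-value near 0.05.

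**The case against.** A reader might infer that the rarer toxicities will never be compared, or that the trial will end with no comparative information on them. The documents do not support that. All TEAEs are described per arm without a frequency floor, SAEs and discontinuation AEs are described with narratives, and laboratory shifts are shown by arm. Counts by arm will exist and a difference can be worked out from them. What is missing is a pre-specified test or interval.

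Other points against the concern:

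- **The rates are assumptions.** This stands. Hepatic reactions in particular could exceed 5% and would then be tested. Section 1 reports liver-enzyme rises with both MF and PM, so a 0% hepatic rate under MF/PM is unlikely, and the smaller loss of 8 to 12 points is the fairer guide there.
- **At 1% to 2% the sample size is the limit, not the cut-off.** This also stands. Power without the cut-off is only about 1% to 13% even against 0%. It is a reason to ask for intervals rather than more tests.
- **Safety is only one reason for the margin, and arm 1 contains no antimonial by design.** True. Nothing in the plan makes the margin conditional on a significant safety result. Safety is still the first reason listed, and the trial's own safety data can quantify it.
- **The 5% may qualify only the word frequent, leaving room for pertinent rare reactions.** Possible, but none is named, so the choice would be made after seeing the data.
- **A separate SAP may settle this.** Section 10.2 refers to one for the definition of major violations. Nothing in the text reviewed says that it names safety outcomes for comparison.

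**Conclusion.** The concern holds as a gap in formal comparison, not as an absence of safety reporting. Section 10.7 ties its only between-arm safety test to reactions above 5%, names no antimonial toxicity, and plans no interval for any safety difference. A toxicity with a true SSG-PM rate below 5% would therefore usually go without formal comparison, and almost always so at 3% or less.

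The size depends on assumed rates. The cut-off matters most at about 3% to 5%, and there mainly for toxicities close to absent under MF/PM. It matters little at 1% to 2%, where 170 per arm cannot support a test in any case. It would be too strong to say that the margin is invalid or that its safety rationale goes unexamined: safety is one of several reasons for the 7%, and the data will be shown by arm. This is a worthwhile, low-cost improvement to the analysis plan.

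**What to change.** In Section 10.7:

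1. Pre-specify, for arm 1 against arm 3 and whatever their frequency: SAEs, AEs leading to treatment discontinuation, and cardiac, hepatic and pancreatic AEs. Other organ classes are optional.
2. Report each as a risk difference with a 95% CI, using a named method suited to small counts, such as Newcombe.
3. Base any ECG-derived comparison on the time points common to both arms, baseline and D14. The schedule of events and Section 8.5 place the D7 and D28 ECGs in SSG-PM only, so using them would build in unequal detection.
4. Take pancreatitis from reported clinical AEs, because amylase and lipase are not among the scheduled laboratory tests (Section 8.5.1).
5. Keep the list of frequent reactions as a second table, defined as above 5% in either arm.

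The cost is SAP wording and a few more table rows from data already being collected. The downside is a few more unadjusted comparisons, which 10.7 already accepts.

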In order to mitigate the low enrollment, the protocol was amended to v3.0 dated 4 May 2018 to include 2 MSF sites (Tabarakallah in Sudan and Abdurafi in Ethiopia). The sites were expected to compensate for the low patient numbers overall. In addition, because of the high proportion of patients in Ethiopia excluded due to severe malnutrition (30-40%), an Ethiopia-specific amendment was implemented to modify the indicator for severe malnutrition from body mass index (BMI) to mid-upper arm circumference (MUAC) to allow for a better representativeness of the Ethiopian population. Finally, active case search and referral networks were initiated at some of the sites. Nevertheless, these measures taken to improve recruitment have not resulted in a significant boost of the enrolment and further actions needed to be taken.

New oral promising NCEs are expected to be at the clinical stage of development for VL patients by 2021 and the plan is to complete this trial before then so that results can be of benefit to the VL patients. Moreover, if new trial(s) with NCEs start before the end of this study, the recruitment of patients will compete with these NCEs studies and will become even more challenging to develop new treatments for visceral leishmaniasis in Eastern Africa region.

Following DSMB review of the available data (meeting held on 7 May 2019), two main changes to the protocol were agreed to achieve completion of the trial in an acceptable timeframe and ensure the achievement of the objectives of the trial. First, to revise the exclusion criteria in order to include a more VL representative population, and second, to discontinue recruitment in the investigational arm 2.

Revision of the exclusion criteria. The reasons for exclusions leading to a low enrollment rate were analyzed. It was noted that across the sites, 15 to 20% of patients were excluded because of laboratory abnormalities. In most cases, the baseline laboratory abnormality was not considered clinically significant by the investigator to indicate AmBisome therapy and a majority of these patients were therefore treated with SSG-PM with a good therapeutic response. For this reason, individual laboratory parameters in the exclusion criteria were replaced by investigator judgement on the need of AmBisome, based on the severity of the clinical manifestations of the disease (such as jaundice, bleeding and oedema) and laboratory parameters.

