Discontinue recrutiment in investigational arm 2 (PM 14d / MF 28 days). Following review of the preliminary available data by the DSMB, including 143 study participants enrolled, among which 135 had completed treatment and Day 28 assessment, and 66 of them had completed their day 210 follow-up visit, it was decided in agreement with the DSMB to ensure retention of the investigational arm 1, on the basis of 1) shorter treatment duration than current standard of care, 2) it can be administered within the hospitalisation period, 3) it is a cheaper option for the control programs, and therefore from a public health perspective will be a potentially more favorable option for patients.

Confidential Page 21 of 68

In this revised protocol version, the analysis remains as planned, but comparison will be performed only between one investigational arm (arm 1 MF/PM 14 days) and the standard of care (SSG-PM). Data from patients randomized in arm 2 (PM 14 days/MF 28 days), which recruitment is now stopped, will be summarized in a descriptive analysis, but will not be included in the comparative hypothesis testing.

The total dose of PM will be 280 mg, similar to the total dose given in the SSG-PM combination therapy (255 mg). For MF, PK data indicated that with 14 days allometric MF treatment, 91% of patients will at least reach EC90 in plasma, which would represent appropriate exposure.

If demonstrated non-inferior to SSG-PM, the 14-day MF-PM regimen will be preferable to be taken forward for future standard of care or alternative treatment to SSG-PM. Data will be presented to Ministry of Health (MoH) and regulatory authorities in the region as evidence to support policy change for the national control programs.

2. Study Objectives and Endpoints

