2.1.2. Secondary Objectives

- To assess the safety of two combination regimens of PM (14 days) and MF (14 or 28 days) with the standard 17-day course of SSG-PM
- To describe the efficacy of the PM (14 days) and MF (28 days) investigational arm
- To describe the pharmacokinetic (PK) profiles of PM and MF (14 days and 28 days regimen) in primary VL patients
- To evaluate parasite clearance in each arm as indicated by direct microscopy and quantitative polymerase chain reaction (qPCR)
- To assess the relationship between PK and PD measurements (parasitological and clinical outcome)
- To describe compliance to MF treatment in an outpatient setting

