The study will be conducted in the LEAP and MSF sites. These sites are located in endemic areas of VL and are reference treatment centers in the regions, where routinely VL patients are diagnosed and treated.

Patients may come to the treatment center passively or through referral from health professionals. Referral can be done on the basis of clinical signs and symptoms and/or rapid diagnostic test. In some of the sites, active case detection is performed by mobile teams visiting regularly highly endemic communities. This procedure will be boosted during the inclusion period of the clinical trial.

Subjects between the ages of 4 and 50 years who fulfill the inclusion / exclusion criteria, and from whom informed consent has been obtained (see 15.1 Informed Consent process) will be enrolled in the study. Patients who have entered screening assessments for this trial will be documented in a Patient Screening/Enrolment Log. Each eligible patient will be assigned a patient identification number by the investigator in the site, sequentially, which will be recorded in the Patient Screening/Enrolment Log.

A note describing the ICF signature and enrolment in the trial will also be made in the patient's file.

Patients were originally randomized centrally to treatment in a 1:1:1 allocation ratio using varying block sizes of 6, 9 or 12 subjects in random order. Following discontinuation of arm 2, a 1:1 allocation ratio is now used with varying block sizes of 4, 6 or 8 subjects. Randomization codes will be prepared by the DNDi Data Center in Nairobi and will be accessible through an online system. If the principal investigator has no internet connection available, randomization codes will also be provided by phone.

Treatment should be started within 7 days after the screening assessment. Otherwise compliance with eligibility criteria has to be reassessed (blood tests).

Enrolment status of subjects at each site will be informed weekly by the sites to the study monitor and updated by data centre. Recruitment will stop once 170 subjects have been enrolled in each trial's arm 1 and 3.

7. Study treatments

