10.2. Definition of study populations included in the analysis

The following patient populations will be defined for analysis:

- Intention-To-Treat (ITT): all randomized patients in the arms to which they were randomly assigned regardless of their adherence with the inclusion-exclusion criteria, the treatment they received, and subsequent withdrawal from treatment or deviation from the protocol.
- Modified Intention-To-Treat (mITT) or Full Analysis Set (FAS): All randomized
 patients receiving at least one dose of treatment. In case of error of treatment
 allocation, the actual treatment received will be used in the analysis. Modified ITT
 set of patients will be used in the primary efficacy analysis and in safety analysis.
- Set of completers: subset of patients belonging to the FAS, who attend the 6-months follow-up visit. This set will be used in a sensitivity analysis of the primary efficacy analysis. This analysis will be based on the definitive cures.
- Per protocol (PP) set of patients: subset of patients belonging to the FAS and who
 are free from major protocol violations. Major protocol violations are any violation
 which might bias the result of the non-inferiority test. Major violations will be defined
 a priori in the statistical analysis plan. They will be identified and documented
 during the blind review of data. This set of patients will be used in the primary
 sensitivity analysis.

The primary population for efficacy analysis at D210 will be the modified intention to treat population (mITT or FAS). Furthermore, per-protocol set of patients and the set of completers sensitivity analyses will be performed.

All patients enrolled in the study and who have been administered the first dose of study medication will be included in the safety analysis.

Confidential Page 54 of 68

For the secondary endpoint on PK, all subjects exposed to at least one dose of the medication and who have a PK sample collected will be included in the analysis.

Patients' data randomized in arm 2 (PM 14 days/MF 28 days), which recruitment is now discontinued, will be summarized in a descriptive analysis, but not included in the comparative efficacy analysis.

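### The safety section as written would test the closed 28-day arm, contrary to Section 1, and sets no rule limiting its comparators to patients randomised while that arm was open

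*Combined protocol and SAP*

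**What the plan says.** Section 10.7 defines the safety set without regard to enrolment period: "All patients enrolled and who received at least one dose of study medication (mITT set of patients) will be included in the safety analysis". It then says "The incidence rate of the most pertinent and frequent ADR (> 5%) of each treatment group will be compared and tested", followed by "No adjustment for multiplicity will be performed". The results feed the benefit-risk assessment. The section names no arm, no pairs, no test and no significance level. It does not restrict comparators to concurrent patients or stratify by period.

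The safety objective in Section 2.1.2 opens "To assess the safety of two combination regimens of PM (14 days) and MF (14 or 28 days" and sets these regimens against the 17-day SSG-PM course, so it covers arm 2. Section 3.1 likewise has the safety of both combination regimens assessed, whereas arm 2 efficacy is only to be described.

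On the formal status of arm 2 the document gives two rules. Section 1 says its data "will be summarized in a descriptive analysis, but will not be included in the comparative hypothesis testing", with no limit to efficacy. Section 10.2 says they "will be summarized in a descriptive analysis, but not included in the comparative efficacy analysis", and the protocol summary is limited to efficacy in the same way.

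Protocol version 4.0 closed arm 2 and widened eligibility together. Section 1 reports that "individual laboratory parameters in the exclusion criteria were replaced by investigator judgement", and Section 6 reports "Following discontinuation of arm 2, a 1:1 allocation ratio is now used", where it had been 1:1:1.

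**The concern.** Randomisation makes arm 2 comparable with arms 1 and 3 only while all three arms were open to the same patients. Patients who entered arms 1 and 3 later came from a different period and under criteria that no longer exclude on individual laboratory values. The parameters concerned (haematology, liver enzymes, bilirubin and creatinine, Section 4.2) are the same ones that are monitored for safety (Section 8.5.1) and shown by arm in shift tables (Section 10.7). Site mix may differ too, because Section 1 says only four of seven sites were actively recruiting early on.

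If arm 2 is tested against, or tabulated beside, the full arm 1 or arm 3, a difference in reaction rates may reflect who was enrolled and when, and not the 28-day regimen. The trial is open label (Section 7.6), so a comparator set chosen after the data are seen would also be open to the charge of being data-driven.

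**Working it through.** **1. Does the plan test arm 2 safety?**

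| Place | Arm 2 in formal comparison? |
|---|---|
| Section 1 | No, without limit to efficacy |
| Protocol summary, Section 10.2 | No, for efficacy; silent on safety tests |
| Section 2.1.2 | Safety of both regimens to be assessed, with SSG-PM named |
| Section 10.7 | Yes on a literal reading (every treatment group, all treated patients) |

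Sections 1 and 10.7 cannot both be followed as worded.

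**2. How much of arms 1 and 3 is non-concurrent?**
Inputs: 170 in each of arms 1 and 3 and about 80 in arm 2 (Section 10.1), with 1:1:1 allocation before closure (Section 6).
- The plan's own total is reproduced: 170 + 170 + 80 = 420.
- Under 1:1:1, arms 1 and 3 each hold about as many patients as arm 2 at closure, so the later share is (170 − n₂)/170.
- n₂ = 80: 90/170 = 53%.
- Range: n₂ = 90 gives 80/170 = 47%; 70 gives 100/170 = 59%; 60 gives 110/170 = 65%.

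**3. What could that do to an arm 2 versus arm 3 test?**
The documents give no reaction rates by period, so every rate here is an assumption. Suppose arms 2 and 3 have the same true rate before closure (p) and arm 3 has rate q afterwards. Then the full arm 3 rate is (80p + 90q)/170, and the spurious difference is (90/170)(q − p).

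The false-positive rate is for a two-proportion z-test with pooled null variance at a two-sided 5% level (assumed, since the plan states none). Worked case, p = 10%, q = 20%:
- Arm 3 rate = (8 + 18)/170 = 15.3%; difference = 5.3 points.
- Overall rate = (8 + 26)/250 = 13.6%; null SE = √[0.136 × 0.864 × (1/80 + 1/170)] = 4.65 points; critical difference = 1.96 × 4.65 = 9.11 points.
- Actual SE = √[0.09/80 + (80 × 0.09 + 90 × 0.16)/170²] = 4.33 points.
- Upper tail: (9.11 − 5.29)/4.33 = 0.88, probability 0.19. The lower tail is negligible.

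| Before (p) | After (q) | Spurious difference | False-positive rate |
|---|---|---|---|
| 10% | 10% | 0 | 5% |
| 10% | 15% | 2.6 points | 8% |
| 10% | 20% | 5.3 points | 19% |
| 20% | 25% | 2.6 points | 7% |
| 20% | 30% | 5.3 points | 14% |

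**4. A milder scenario, from eligibility alone.**
Section 1 says 15 to 20% of patients were excluded for laboratory abnormalities. Assume that this is also their share of later enrolment and that their risk is 20% against 10% in others.
- 0.15 to 0.20 × 90 = about 14 to 18 patients, or 8 to 11% of arm 3.
- Shift = 0.08 to 0.11 × 10 points = 0.8 to 1.1 points. The same test then rejects in just over 5% of trials.

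The stated share is of patients excluded, not of patients later enrolled. Suppose instead that it is a share of confirmed cases, of which 16% were enrolled (Section 1), and that half of the formerly excluded now enter. Their share of later enrolment is then 7.5/23.5 to 10/26, or 32 to 38%, and the shift is 1.7 to 2.0 points.

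**5. What does restriction cost in precision?**
SE of the difference = √[p(1 − p)(1/n₂ + 1/n₃)].
- p = 20%: 5.4 points for 80 versus 170; 6.3 points for 80 versus 80.
- p = 10%: 4.1 points for 80 versus 170; 4.7 points for 80 versus 80.

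**The case against.** A reader might infer that the plan does test arm 2 against all of arm 3, and that arm 2 would come out looking safer. The documents support neither statement.

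- **The test.** Section 10.7 names neither arm 2 nor any pair of arms, Section 2.1.2 speaks of assessing and not of testing, and Section 1 excludes arm 2 from hypothesis testing. Section 10.2 also refers to a statistical analysis plan for further definitions, and the safety contrasts may be set there. This part stands: the finding is a conflict plus a missing rule, not a declared faulty test.
- **The direction.** Under Sections 8.6.1 and 8.6.2, conditions present at entry that do not worsen are not adverse events, and abnormalities expected from the disease are generally not reported. Severe disease and haemoglobin below 5 g/dl still exclude (Section 4.2). Section 1 says that in most cases the excluding abnormality was not judged clinically significant enough to indicate AmBisome. This stands too.
- **The size.** In the milder scenario the bias is about 1 point against an SE of 4.1. Total error is then √(4.1² + 1.1²) = 4.2 points without restriction and 4.7 with it. At a 10% rate, restriction lowers total error only if the bias exceeds √(4.74² − 4.07²) = 2.4 points. So restriction is not free. What it secures is a comparison that randomisation protects, whatever the later rates turn out to be.

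The objection does not remove the conflict between sections. Nor does it cover side-by-side descriptive tables, which would mix periods even if nothing is tested.

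**Conclusion.** The point holds as a matter of reconciliation and specification. Section 10.7 as worded takes arm 2 into the safety tests, Section 1 takes it out, and nothing limits arm 2 comparators to concurrent patients. About 53% of each of arms 1 and 3 is non-concurrent with arm 2 (47 to 65% for arm 2 sizes of 90 down to 60). This rests on the stated targets and on near-equal arms under 1:1:1.

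Bias in an arm 2 contrast is possible, but its sign and size cannot be derived. The illustrations run from about 1 point, with hardly any effect on the error rate, to 5.3 points with 14 to 19% false positives, and all of them rest on assumed rates. The closure and the eligibility change may not have taken effect together at every site, because Section 13 makes amendments wait for ethics approval, so their overlap is approximate.

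Arm 1 versus arm 3 is randomised concurrently throughout, so its safety comparison and the primary efficacy analysis are untouched. Only the 14-day regimen is meant to go forward (Section 1), which limits the consequence. This is a cheap improvement.

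**What to change.** In Section 10.7 and the statistical analysis plan, choose one rule and align Sections 1, 2.1.2, 10.2 and 10.7 with it:

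1. Arm 2 safety is descriptive only and outside the safety hypothesis tests, as Section 1 already says. This is the simpler choice.
2. Or, if arm 2 is compared, every arm 2 contrast uses only arm 1 and arm 3 patients randomised under the 1:1:1 scheme, or is stratified by that period. In a Mantel-Haenszel analysis of arm 2 against one other arm, the later stratum has no arm 2 patients and so no weight, which makes the two options equivalent there.

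Under either rule, show arm 2 descriptive tables, including its efficacy, beside the concurrent arm 1 and arm 3 patients. Define concurrency by the allocation scheme and protocol version in force at the site when the patient was randomised, not by one calendar date. Leave the arm 1 versus arm 3 comparison on the full set, and name the pairs, the test and the level in Section 10.7.

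The cost is one period flag and a text change. Arm 2 contrasts become about 80 versus 80, with the loss of precision shown in step 5 of the working.
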